13.2. Analysis of Outcome Measures

A separate Statistical Analysis Plan will be produced and will provide a more comprehensive description of the planned statistical analyses. A brief outline of these analyses is given below. The primary comparison groups will be composed of those treated with laparoscopic hysterectomy versus those treated with open, abdominal hysterectomy. For all outcomes, analyses will be based on the intention to treat principle, i.e. all participants will be analysed in the treatment group to which they were randomised irrespective of compliance or other protocol deviation. For the primary outcome, given the nature of the non-inferiority design, supportive per-protocol and CACE analyses³⁸ will be considered alongside the intention-to-treat population. All outcomes will be adjusted for the minimisation variables listed in Section 6.3 where possible.

For all major outcome measures, summary statistics and differences between groups, e.g. relative risks, will be presented with 95% confidence intervals. For the primary outcome, this is equivalent to a one-sided 97.5% confidence interval and hence

conservative in terms of the non-inferiority margin. For the trial to declare non-inferiority of the laparoscopic approach, the lower margin of the absolute risk difference (see 13.2.1 for calculation method) confidence interval must not exceed 3%.

For the key secondary outcome of time from surgery to resumption of usual activities, we will incorporate a conditional hierarchical approach to interpretation of the 95% confidence interval to ensure we appropriately control for the overall rate of type I error³⁹. If the primary outcome meets its non-inferiority objective we will then proceed to examine any differences between the two approaches for this outcome. For example, if the 95% confidence interval does not contain 1 (and favours laparoscopic) we will declare superiority of the laparoscopic approach.

Other secondary outcomes will be considered as exploratory; no adjustment for multiple comparisons will be made and hence significance should not be inferred from the confidence interval width. The exception is Serious Adverse Events may be subject to statistical testing without adjustment for multiple testing, as adjustment for multiplicity is counterproductive for considerations of safety.³⁹

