8.3. Participant Withdrawal

Informed consent is defined as the process of learning the key facts about a clinical trial before deciding whether or not to participate. It is a continuous and dynamic process and participants should be asked about their ongoing willingness to continue participation.

Participants should be aware at the beginning that they can freely withdraw (discontinue participation) from the trial (or part of) at any time.

LAVA has adopted an analysis based on a modified intention to treat principle, i.e. all participants will be followed up and analysed in the treatment group to which they were randomised provided a hysterectomy (of any type) was undertaken unless they withdraw from the study.

Types of withdrawal as defined are:

- a) If for any reason the participant has not undergone a hysterectomy of any type they will be considered to have withdrawn from the study and not be followed up
- b) The participant would like to withdraw from the allocated trial treatment pathway but is still having a hysterectomy of any type, and does not wish to attend trial visits in accordance with the schedule of assessments but is willing to be followed up at standard clinic visits and if applicable using any central UK NHS bodies for long-term outcomes (i.e. the participant has agreed that data can be collected at standard clinic visits and used in the trial analysis, including data collected as part of long-term outcomes)
- c) The participant would like to withdraw from trial treatment but is still having a hysterectomy of any type, and is not willing to be followed up in any way for the purposes of the trial and for no further data to be collected (i.e. only data collected prior to the withdrawal can be used in the trial analysis)

or

- d) The participant wishes to withdraw completely from the trial (i.e. from trial treatment and all follow up) and is not willing to have any of their data, including that already collected, to be used in any future trial analysis

*If the participant wishes to withdraw from the allocated trial treatment pathway but is still having a hysterectomy of any type, and is willing to be followed up in accordance with the schedule of assessments and if applicable using any central UK NHS bodies for long-term outcomes (i.e. the participant has agreed that data can be collected and used in the trial analysis), they will **not** be considered as being withdrawn from the study*

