13. STATISTICAL CONSIDERATIONS

13.1. Sample Size

To enable 90% power to test the non-inferiority hypothesis at a one-sided 2.5% significance level (two-sided 5% level) assuming a 3% margin of non-inferiority and a major surgical complication rate of 6% in the abdominal (control) group requires 2634 participants. The estimate of 6% is taken from a similar previous comparative study.¹¹ A 3% margin is justifiable because of the trade-off of potentially swifter recovery with laparoscopic surgery; a view shared by our patient focus group and is substantially less than the 5% difference observed in the previous major trial,¹¹ which led to the continued use of open abdominal hysterectomy.

An extra consideration is the potential for clustering by surgeon due to the expertise based design.^{19 34} Under the assumption that each of the 50 centres will utilise 6 surgeons (operating on approximately 9 patients on average during the study), along with an intra-cluster correlation (ICC) estimate of 0.02, the sample size has been increased by 16% to 3055. This ICC estimate used - in the absence of precise estimates - is considered conservative given the outcome is clinical and of low prevalence, both of which are factors associated with low ICC.^{35, 36} However, even varying these factors up to an ICC of 0.07 or average cluster size of 29, shows we will have at least 80% power to establish non-inferiority in these situations.

A final inflation of 6% to account for loss to follow-up (similar to the aforementioned previous study) brings the final sample size total to 3250 participants. This size of sample would give the ability to detect meaningful differences between groups in our key secondary outcome of time from surgery to resumption of usual activities. Assuming the median recovery time in the abdominal group is between 6 and 9 weeks³⁷ we will have high levels of power (>90%) to detect reductions of 1 week in all cases.

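### Protocol sections 13.2 and 8.3 define the main analysis population differently, and rule 8.3(a) stops the data collection that the 13.2 definition needs

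*Protocol*

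**What the plan says.** Section 13.2 (Analysis of Outcome Measures) opens with "The primary comparison groups will be composed of those treated with laparoscopic hysterectomy versus those treated with open, abdominal hysterectomy". The next sentence sets intention to treat for all outcomes and explains it: "all participants will be analysed in the treatment group to which they were randomised irrespective of compliance or other protocol deviation". Per-protocol and CACE analyses of the primary outcome are then named as supportive.

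Section 8.3 (Participant Withdrawal) states: "LAVA has adopted an analysis based on a modified intention to treat principle". Participants are followed up and analysed in the group "to which they were randomised provided a hysterectomy (of any type) was undertaken unless they withdraw from the study". Rule (a) of the same section covers a woman who for any reason "has not undergone a hysterectomy of any type they will be considered to have withdrawn from the study and not be followed up".

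Section 13.1 (Sample Size) applies "A final inflation of 6% to account for loss to follow-up" and does not say whether women without a hysterectomy are counted in it.

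**The concern.** The protocol fixes its analysis population in two sections, and they differ on women who are randomised but have no hysterectomy. Under 13.2 these women are in; under 8.3 they are out. This is more than detail for a statistical analysis plan. Such a plan can choose between the definitions, but it cannot restore data that rule 8.3(a) tells sites not to collect.

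The exclusion happens after randomisation in a trial where bias by arm is possible. Allocation is open (6.5), another surgeon in the unit may operate (7.1, note 4), and treatment may change for medical reasons or at the woman's request (7.3). Women who drop out before surgery may therefore differ between arms in number and kind. At stake are a clear primary population for the non-inferiority claim, the completeness of primary events, and the all-randomised basis of the EQ-5D and QALY results.

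**Working it through.** **1. Three women under each statement**

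| Woman | 13.2, intention to treat | 8.3, modified intention to treat | 13.2, *treated with* read literally |
|---|---|---|---|
| Allocated laparoscopic, has open hysterectomy | Laparoscopic | Laparoscopic | Open |
| Never operated on | Allocated arm | Excluded, not followed up | Neither group |
| Anaesthesia or surgery begins, event occurs, hysterectomy abandoned | Allocated arm, with her event | Excluded on the wording of rule (a) | Neither group |

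The first row differs only under the literal reading of one sentence. The other two rows are a firm conflict between 13.2 and 8.3.

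**2. Can rule (a) remove a primary event?** Yes. Section 8.1.2 counts major anaesthetic events, anaphylaxis among them, as primary events. Section 9.4 starts protocol treatment at entry to the anaesthesia suite. A woman can therefore have a qualifying event without completing a hysterectomy. Adverse event reporting is no safety net, because 9.2 leaves anaesthetic and surgical complications to the CRFs. With 3055 analysed, an arm holds 3055/2 = 1527.5 women, so each lost event moves that arm's rate by 1/1527.5, about 0.07 percentage points, against a 3-point margin. The protocol gives no rate for abandoned operations.

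**3. Can the 13.2 analysis be done for EQ-5D and QALYs?** Not for these women. After baseline, EQ-5D is collected at 6 weeks, 12 weeks and 12 months post-surgery (8.2.7 to 8.2.9), and rule (a) stops follow-up. Section 15 times cost per QALY from surgery in one place and from randomisation in another. The second timing includes women who are never operated on.

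**4. The protocol's sample size, reproduced.** Inputs from 13.1: 6% in both arms, 3-point margin, one-sided 2.5%, 90% power, ICC 0.02, 9 patients per surgeon, 6% loss.

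- Per arm: (1.960 + 1.282)² × 2 × 0.06 × 0.94 / 0.03² = 1317, so 2634 in total.
- Design effect: 1 + (9 − 1) × 0.02 = 1.16, and 2634 × 1.16 = 3055.
- Loss: 3055 / 0.94 = 3250.

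All three figures agree with the protocol.

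**5. If non-operated women are excluded on top of the 6%.** The share q is an assumption. N = 3250 × 0.94 × (1 − q); standard error = √(2 × 0.06 × 0.94 / (N / (2 × 1.16))); power = Φ(0.03 / standard error − 1.96).

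| q | N analysed | Power |
|---|---|---|
| 0% | 3055 | 90.0% |
| 2% | 2994 | 89.4% |
| 5% | 2902 | 88.5% |
| 10% | 2750 | 86.8% |

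If the 6% already covers these women, the first row applies and 3250 stands.

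**6. If they are kept and scored event-free.** Take a true excess of exactly 3 points among operated women (9% v 6%), with 3055 analysed and the same design effect. Both rates are multiplied by (1 − q).

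| q | Observed excess | Chance of declaring non-inferiority |
|---|---|---|
| 0% | 3.00 points | 2.5% |
| 2% | 2.94 points | 2.9% |
| 5% | 2.85 points | 3.5% |
| 10% | 2.70 points | 4.9% |

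The two definitions therefore err differently: exclusion costs some power, and event-free scoring weakens error control for operated women.

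**The case against.** The strongest defence is that the conflict hardly touches the primary analysis. The outcome runs to six weeks after surgery, so a woman with no operation has no outcome window. Section 13.2.4 also leaves missing primary outcomes out of the first analysis. Unless non-operated women are scored event-free, the analysed sets nearly coincide, and restricting the primary set to operated women is defensible. This largely stands for women never taken to theatre. It does not answer the abandoned operation with an event, or the outcomes for which 13.2 promises all participants.

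Bias is also partly checkable. Baseline data precede randomisation (8.2.2), the date, reason and type of withdrawal are recorded (8.3), and imputation and tipping-point analyses are foreseen (13.2.4). This stands too, but unrecorded EQ-5D values remain unrecorded.

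A reader might infer two stronger points that the protocol does not support:

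- *That an as-treated primary analysis is planned, biased by route changes.* The sentence after *treated with* assigns women by randomisation for all outcomes, 8.3 does the same, and analyses that take account of compliance are supportive only. An estimate of as-treated bias would describe no planned analysis, so none is given.
- *That the 6% inflation leaves these women out.* Rule (a) classes them as withdrawn and not followed up, so they may fall within the 6%. Section 7.3 expects withdrawal before treatment to be exceptional.

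**Conclusion.** The point holds as a contradiction between 13.2 (all randomised) and 8.3 (randomised and had a hysterectomy), with two practical consequences of rule (a): EQ-5D and QALY data are lost for non-operated women, and a woman with a primary event before an abandoned hysterectomy can be excluded. The *treated with* sentence is a drafting fault to correct, not a third planned population.

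The size is probably modest. The sample size calculation is correct. The figures of 88.5% and 86.8% power assume 5% and 10% not operated on beyond the 6% loss. The error rates of 3.5% and 4.9% assume the same shares scored event-free. The protocol gives no rate of non-operation, so all four are illustrations. Severity is should-fix. The part that cannot wait for an analysis plan is rule (a), because follow-up not collected cannot be recovered.

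**What to change.** 1. In 13.2, replace *treated with* by *randomised to*.
2. State one primary population in identical words in 8.3 and 13.2, by randomised arm. If it is restricted to operated women, call it modified intention to treat and include every woman whose anaesthesia or surgery began, with her actual events.
3. Report numbers and reasons for non-operation by arm.
4. Add an all-randomised sensitivity analysis of the primary outcome, using the tipping-point method already planned. Any event-free scoring should apply only to women whose anaesthesia never began.
5. Amend 8.3(a) so that non-operated women are not automatically withdrawn, but are asked for at least the EQ-5D at a stated time from randomisation unless they refuse.

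The cost is protocol wording, one sensitivity analysis and a few extra questionnaires. Item 5 also needs a time anchor, because follow-up is now scheduled from surgery and adverse event reporting starts at the anaesthesia suite.

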1.2.4. Research question

The research question has been framed as follows: What is the clinical and cost effectiveness of laparoscopic surgery compared to open abdominal hysterectomy for women with a benign gynaecological condition undergoing a hysterectomy?

- Population: Women with a benign gynaecological condition requiring a hysterectomy
- Intervention: Laparoscopic hysterectomy
- Comparator: Open abdominal hysterectomy
- Primary outcome: Major surgical complications

Current evidence-based guidance and recent systematic reviews have acknowledged the need for clinical trials to inform clinicians and patients regarding the relative merits of the route of hysterectomy⁴. Contemporary gynaecological practice has developed rapidly in response to technological advances facilitating less invasive surgical techniques for common operations aligned with innovations in pre, peri- and post-operative care designed to 'enhance' recovery²⁰. The results of this trial will have a significant impact on day-to-day clinical practice in women's health care.

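### The non-inferiority rule names the wrong confidence limit: read literally, it would usually declare laparoscopic surgery non-inferior when its true complication excess equals or exceeds the 3-point margin

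*Protocol*

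**What the plan says.** Section 13.2 gives the success criterion for the primary outcome: non-inferiority of the laparoscopic approach is declared on condition that "the lower margin of the absolute risk difference (see 13.2.1 for calculation method) confidence interval must not exceed 3" per cent. The interval is the two-sided 95% interval for the absolute risk difference from the model in section 13.2.1.

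Three other statements fix the context.

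- The outcome is an adverse one. Section 1.2.4 gives "Primary outcome: Major surgical complications", so a higher rate is worse.
- The only order of comparison stated is in section 13.2: "those treated with laparoscopic hysterectomy versus those treated with open, abdominal hysterectomy". The protocol never says which arm is subtracted from which, and the 3% carries no minus sign.
- Section 13.1 sizes the trial "at a one-sided 2.5% significance level (two-sided 5% level"), with 90% power, "assuming a 3% margin of non-inferiority and a major surgical complication rate of 6% in the abdominal (control) group requires 2634 participants".

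Section 13.2 then makes the test of the key secondary outcome, time to resumption of usual activities, conditional on the primary outcome meeting its non-inferiority objective.

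**The concern.** For a harmful outcome with a 3-point margin there are two equivalent correct rules:

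- laparoscopic minus abdominal: the **upper** limit lies below +3 points;
- abdominal minus laparoscopic: the **lower** limit lies above −3 points.

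The written rule pairs the lower limit with +3 and asks that it not be exceeded. Taken literally, this matches neither. On laparoscopic minus abdominal it looks at the favourable end of the interval, and fails only when the whole interval lies above the margin. It therefore treats failure to prove an excess beyond 3 points as proof that there is none.

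This rule decides the trial's conclusion. The one-sided 2.5% error rate of section 13.1 does not apply to it as worded. The error control claimed for the key secondary outcome also depends on it, because that outcome is tested only after the primary criterion is met.

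**Working it through.** **Inputs.** From section 13.1: margin 0.03; control rate p0 = 0.06; one-sided 2.5% (z = 1.960); 90% power (z = 1.2816); 16% inflation for clustering; 6% loss to follow-up. From section 6.3: 1:1 allocation. The laparoscopic rate is not stated; for the sample size it is assumed equal to control, 6%.

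**1. Reproduce the plan's figure.** Standard test of the unfavourable limit:

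n per arm = (1.960 + 1.2816)² × (0.06×0.94 + 0.06×0.94) / 0.03² = 10.507 × 0.1128 / 0.0009 ≈ 1317, so 2634 in total, as stated.

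Design effect 1 + (9 − 1) × 0.02 = 1.16; 2634 × 1.16 ≈ 3055; 3055 / 0.94 = 3250. All three stated totals are reproduced. After clustering, the effective size is 3055 / 1.16 / 2 ≈ 1317 per arm, which is used below.

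**2. Probability that each rule declares non-inferiority.** Let RD be the true difference, laparoscopic minus abdominal, p1 = 0.06 + RD, and SE = √[(p0(1 − p0) + p1(1 − p1)) / 1317]. With a normal approximation:

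- literal rule (lower limit ≤ +0.03): Φ((0.03 − RD)/SE + 1.96)
- upper-limit rule (upper limit < +0.03): Φ((0.03 − RD)/SE − 1.96)

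| True excess | SE | Literal rule | Upper-limit rule |
|---|---|---|---|
| 0 points | 0.00925 | about 100% | 90.0% |
| 3 points (the margin) | 0.01025 | 97.5% | 2.5% |
| 4 points | 0.01054 | 84.4% | 0.2% |
| 5 points | 0.01082 | 54.5% | about 0.01% |
| 6 points | 0.01109 | 22.8% | below 0.01% |

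Worked line, 5 points: (0.03 − 0.05)/0.01082 ≈ −1.85. Adding 1.96 gives 0.11, so Φ ≈ 0.545. Subtracting 1.96 gives −3.81, so Φ ≈ 0.0001.

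The upper-limit rule returns the 90% power and 2.5% error that section 13.1 claims. The literal rule does not.

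**3. One trial result.** Observed 10% versus 6%: 0.04 ± 1.96 × 0.01054, that is +1.9 to +6.1 points. The whole interval is above zero, yet its lower limit is under +3, so the literal rule is met.

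**4. Largest observed excess that passes**, with control at 6%. Solving d = 0.03 + 1.96 × SE(d) gives about 5.1 points for the literal rule. Solving d = 0.03 − 1.96 × SE(d) gives about 1.1 points for the upper-limit rule.

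**5. Opposite subtraction, still literal** (lower limit of abdominal minus laparoscopic ≤ +0.03): Φ((0.03 + RD)/SE + 1.96), which is essentially 100% at every excess from 0 to 6 points.

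**The case against.** The strongest reply is that the sentence can be read correctly. Take the difference as abdominal minus laparoscopic, so that the lower limit is the unfavourable one, and take exceeding 3% to mean going beyond the margin, below −3 points. That reading gives 90% power at no difference and 2.5% error at the margin. The intended test can also be recovered from section 13.1, whose figures follow exactly from it. That section describes 3% as well under the 5% difference in the previous major trial, a purpose at odds with a rule that passes a true 5-point excess about half the time. The protocol calls its analysis section a brief outline, and a sign convention is often settled in the SAP.

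Much of this stands. The error is probably one of drafting, and nothing suggests the trial team means to test the favourable limit. The error rates above therefore describe the sentence taken literally; they are not a forecast of the trial's conduct. Nor does the literal rule pass everything on laparoscopic minus abdominal: it fails when the whole interval lies above 3 points.

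It does not rescue the wording. The reading needs both a reversed subtraction and a minus sign, and the protocol has neither; the one order it states points the other way. Leaving the sign convention to the SAP would be acceptable had the protocol left the rule open, but it states the rule. A SAP with the correct rule would then conflict with the protocol on the primary criterion.

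**Conclusion.** The concern holds: the decision rule in section 13.2 is wrong as written and inconsistent with the test in section 13.1. At a true excess equal to the margin, the literal rule declares non-inferiority 97.5% of the time instead of 2.5%. At 5 points, the difference that section 13.1 links to the continued use of open surgery, it does so 54.5% of the time instead of about 0.01%.

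These figures assume a 6% control rate, 3055 women analysed with a design effect of 1.16, laparoscopic minus abdominal, and an unadjusted normal approximation; covariate adjustment is ignored. Other plausible inputs would move the values away from the margin, but not the main result: under this approximation, testing the opposite limit turns a 2.5% error at the margin into 97.5%. The sample size itself is sound. This should be corrected before any unblinded comparison of the primary outcome, so that there can be no dispute over which rule was prespecified.

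**What to change.** Replace the sentence in section 13.2 with: *The risk difference is laparoscopic minus abdominal. Non-inferiority is declared if the upper limit of the two-sided 95% confidence interval is below +3 percentage points.*

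The SAP and DMC charter were not seen, so nothing is claimed about their wording; check that wherever they state the rule they use the same order, limit and sign.

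The cost is one sentence in a protocol amendment. Sample size, data collection and model are unchanged.
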